Objectives: To evaluate the impact of LSQ on (1) participation in physical therapy using Pittsburg Rehabilitation Participation Scale; (2) quality of life using Quality of Life – Alzheimer’s Disease Scale (participant’s version); and (3) depression symptoms using Cornell Scale for Depression in Dementia (CSDD).

Methods: A consecutive sample of convenience of up to 60 patients with mild to moderate cognitive impairment with 44 (22 per group) completing the study will be recruited from a nursing home facility. Patients will be randomly allocated in two groups: (1) *Control group*, which will receive standard physical therapy care without LSQ use; and (2) *Experimental group*, where physical therapists will use the LSQ. Each patient’s family member will receive a LSQ to complete prior to the start of the intervention. Patients’ participation, quality of life and depression symptoms will be measured on day 1 and again after 3 weeks (mid-term), and 6 weeks of intervention. Quality of life and depression symptoms will also be measured 6 weeks following intervention. A licensed occupational therapist blinded to the participants’ group allocation will measure all three dependent variables

Statistical Analysis: Descriptive statistics including means, standard deviations, frequency counts, median, mode, variance and frequency counts will be used to assess sample demographics. The Rank Sum test will be used to assess differences in Pittsburg Rehabilitation Participation Scale between the intervention and control group. Spearman Rank correlations will be used to determine the strength of the correlation between Mini-Mental state examination, Pittsburg Rehabilitation Participation Scale and Quality of Life Alzheimer Disease.

Key words: Dementia, Life story questionnaire, Physical therapy, Participation, exercise

Financial Disclosure and Conflict of Interest: The investigators affirm that they have no financial affiliation (including research funding) or involvement with any

commercial organization that has a direct financial interest in any matter included in this manuscript.

NON-SCIENTIFIC ABSTRACT

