Aims: The study plans to evaluate the impact of LSQ use on participation in physical therapy, quality of life and depression symptoms in people with cognitive impairment. The intervention will include gathering LSQ information for selected subjects from family patient/family members and then using this information for 6 weeks to evaluate the impact of LSQ on (1) participation in physical therapy using the Pittsburg Rehabilitation Participation Scale (Appendix B); (2) quality of life using the Quality of Life – Alzheimer’s Disease Scale (participant’s version) (Appendix C); and (3) depression symptoms using the Cornell Scale for Depression in Dementia (CSDD) (Appendix D).

Value: Previous studies demonstrated psychosocial life story book usage benefitted people with dementia in nursing homes, their relatives, and staff¹²⁻¹⁴. As per Woods et al. the life story book is beneficial to improve cognitive function, communication, quality of life and mood. However, randomized comparison trials are needed to evaluate the effect of life story book usage on physical therapy participation. People with dementia demonstrate challenges in physical therapy participation due to poor cognition and communication. Physical therapists are challenged to develop plans of care for people with dementia due to poor cognition. The LSQ can help develop individualized and person-centered care. It is hypothesized that the LSQ will help increase physical therapy participation for

Dementia - Life Story Questionnaire – Physical Therapy

people with cognitive impairment and therefore improve their functional mobility, activities of daily living, depression symptoms and quality of life. If LSQ proposed benefits are substantiated, this study could be the first to highlight the importance of LSQ increasing physical therapy participation and improving depression symptoms and quality of life in patients with cognitive impairment.

RESEARCH QUESTIONS, HYPOTHESES AND VARIABLES

RESEARCH QUESTION(s) (RQs)-This project aims to answer the following research questions:

1. **RQ 1:** What is the effect of LSQ usage on physical therapy participation in people with cognitive impairment at 3 weeks(mid-term) and six weeks as compared to a control group?
2. **RQ 2:** What is the effect of LSQ usage on quality of life in people with cognitive impairment at 3 weeks(mid-term), six weeks and six weeks following intervention as compared to a control group?

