3. **RQ 3:** What is the effect of LSQ usage on depression in people with cognitive impairment at 3 weeks(mid-term), six weeks and six weeks following intervention as compared to a control group?
4. **RQ 4:** What is the relationship between cognitive impairment severity and physical therapy participation improvement at the end of the intervention (6 weeks)?

RESEARCH HYPOTHESES -This student has devised the following research experimental hypotheses

1. **Research Hypothesis 1:** LSQ usage will increase physical therapy participation in people with cognitive impairment at 3 weeks(mid-term) and six weeks as compared to a control group.

2. **Research Hypothesis 2:** LSQ usage will improve symptoms of depression in people with cognitive impairment at 3 weeks(mid-term), six weeks and six weeks following intervention as compared to a control group
3. **Research Hypothesis 3:** LSQ usage will improve quality of life in people with cognitive impairment at 3 weeks(mid-term), six weeks and six weeks following intervention as compared to a control group.
4. **Research Hypothesis 4:** Mild cognitive impairment will be positively associated with participation in physical therapy at six weeks following LSQ usage as compared to a control group.

COMPARISON VARIABLES

Independent Variable(s)-The student plans to use the following Independent Variable(s) (IV)

1. IV1: physical therapist use of LSQ
 - a. Level 1: LSQ usage
 - b. Level 2: no LSQ usage

Dependent Variable(s)-The Student plans to measure the following dependent variable(s) (DV)

1. DV1: Pittsburg Rehabilitation Participation Scale²⁵(Appendix B)
2. DV2: Quality of Life (quality of life - Alzheimer's disease scale - participant's version)²⁶(Appendix C)

3. DV3: Depression (Cornell Scale for Depression in Dementia (CSDD)²⁷(Appendix D)

Relationship Variable(s)- The investigator plans to use the following variables (RV) for RQ 4

1. RV1: Pittsburg Rehabilitation Participation Scale²⁵(Appendix B)
2. RV2: Mini-mental state of examination (MMSE)^{22,23} = Measure of dementia severity³ (Appendix E)

METHODS

Research Design

Prospective Randomized Control Trial. The trial will be registered on Clinicaltrials.gov.

Research Setting/Location

Peachtree Place (Dementia care facility), Weatherford, Texas. This study will be approved by Texas Tech University (TTU) Institutional Review Board (Lubbock Campus).

Power Analysis

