Power calculations were performed to determine the sample size required for the study using the Pittsburgh participation in rehabilitation scale as the primary outcome measure and calculations using Mann-Whitney U test. The study was designed with α value set at 0.05 and Power set at 0.8 (β set at 0.2). The effect size was calculated using G*Power (version 3.1) using differences in the Pittsburgh participation in rehabilitation scale between the experimental versus the control group of 0.5 with a standard deviation of 0.5, based on pilot testing conducted at Peachtree Place, which resulted in effect size of 1 and a sample size of 44 (22 participants in each group) (<http://www.gpower.hhu.de/>).

Sampling

A consecutive sample of convenience of up to 60 patients (44 patients = 22 per group completing the study) with MMSE scale score between 10-18 (moderate cognitive impairment) and 19-23 (mild cognitive impairment), and residing at the Peachtree Place dementia care facility in Weatherford Texas will

be recruited. Patients (or their families) will be asked to participate after explanation of the study.

Subjects

Inclusion Criteria: (1) Patients residing in Peachtree Place in Weatherford, Texas; (2) Age 60-89 years; (2) Diagnosis of dementia disease, in mild to moderate stage using the MMSE (score between 10-23)^{22,23} and (3) attendance to physical therapy for 6 weeks.

Exclusion Criteria: (1) Unable to speak English; (2) blindness; (3) deafness; (4) MMSE score >23 and (5) history of major psychiatric disorder such as schizophrenia and bipolar disorder that required hospital admission within the last year.

Sequence

Reliability Testing

Investigator 2, who is a licensed occupational therapist with 15 years of clinical experience in geriatric population care, will be educated to collect the three dependent variables including the Pittsburg Rehabilitation Participation scale, the quality of life -Alzheimer's disease scale and the Cornell Scale of Depression in Dementia (CSDD) scale to establish intra-rater reliability.

Investigator 1 who is the principal investigator and a licensed physical therapist with 10-year experience treating geriatric population and has experience in using the Pittsburg Rehabilitation Participation scale, the quality of life -Alzheimer's disease scale and the CSDD scale, will explain and educate Investigator 2 in

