each scale usage. After demonstration, Investigator 2 will record the three dependent variables measurements on the same patients twice, with at least 48hour interval between measurements. A minimum of five patients will be used. The intra-rater reliability of measurements on the two separate days will be calculated.

Study Sequence

Investigator 1 will conduct patients' screening (Appendix F) before they enroll the study to determine their eligibility. Participants with mild cognitive impairment (MMSE 19-23) demonstrating understanding of the research and the consent decision and indicating a willingness to take part will be asked to sign a consent form. For participants with moderate cognitive impairment (MMSE 10-18), both the potential participants and their legally authorized representatives will be asked to give consent to allow study participation.

Patients will be randomly assigned using block randomization with a 1:1 allocation ratio and randomly permuted block sizes of 2 to 6 based on severity of cognitive impairment. The randomization will be performed in R software (version 4.1.2, R Core Team) using the randomize R package (version 2.0). Each subject will be randomized to one of two interventions: (1) Control group, which will receive standard physical therapy care without LSQ use; and (2) Experimental group, where physical therapists will use the LSQ. The randomization file will be generated by Investigator 1 (Physical therapist) not involved in the data collection process, with the results stored in a spreadsheet accessible only to the investigator responsible for the subjects' group assignment. This investigator will

not participate in any data collection. Due to the nature of the study, participants will not be blinded to the group assignment and to the treatment they will receive. Investigator 2 measuring the dependent variables, however, will be blinded to the group assignment.

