Family members of each patient will receive an LSQ to complete prior to the start of the intervention (Appendix A). Investigator 1 will conduct all physical therapy sessions for the study patients. Investigator 2, will collect the following dependent variables on day 1 of week 1, and on day 1 of third and sixth weeks:(1) Pittsburg Rehabilitation Participation Scale, which measures patients' participation in therapy; (2) Quality of Life - Alzheimer's disease scale; and (3) depression symptoms (Cornell Scale for Depression in Dementia). Additionally, Investigator 2 will record quality of life and depression at six-week following the intervention. Both investigators will enter their data using Texas Tech University Health Sciences Center password protected Qualtrics platform.

Both control and intervention groups will receive individual exercises that include strengthening, balance, gait, aerobic, endurance, dual cognitive motor tasks and exercises to improve activities of daily living and functional mobility²⁸. A pragmatic exercise program will be used for each participant needs based on physical therapy evaluation and goals. Each session will last approximately 60 minutes with five minutes warm up and five minutes cool down, three to five times per week for six weeks.

All patients will be charged for physical therapy services provided, as these services are standard of care, but there will be no charge for the LSQ use.

Upon completion of the trial, if LSQ results in outcomes improvements, the control group will receive six weeks of physical therapy using LSQ. All licensed therapists who participate in this research completed the Collaborative Institutional Training Initiative (CITI) training.

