Example of LSQ usage: [name] has been diagnosed with dementia and scores 15 (Mild Cognitive Impairment) on MMSE scale. His family has completed LSQ and submitted it to the facility. All Peach Tree Place employees have access to LSQ to facilitate patient care. Patient's LSQ mentioned that patient loves coffee, enjoys playing cards and likes everything about cars. This patient is always excited to come to therapy when physical and occupational therapists (clinicians) mention drinking coffee together. Once patient arrives in therapy room, the clinician plays different card games with this patient in standing, to improve standing tolerance, also use balance board to challenge standing balance and to facilitate functional mobility. The clinician talks about cars, shows variety of car magazines while working on leg exercises. So, this clinician used various information from LSQ for this patient to motivate and improve therapy participation.

Outcome Assessment:

1. Pittsburgh rehabilitation participation scale (Appendix B) – to measure participant's participation in physical therapy
2. Quality of life in Alzheimer's disease – participant's version (Appendix C) – to access quality of life in dementia participants

3. Cornell scale for depression in dementia (Appendix D) – to access depression symptoms in dementia participants

Data Analysis

Descriptive statistics (means, medians, modes, standard deviations, frequency counts, minimum and maximum values) will be calculated using Excel version 2017 and SPSS version 20 (IBM Corp. Released 2011. IBM SPSS Statistics for Windows, Version 20.0. Armonk, NY: IBM Corp.) for the subjects' characteristics including age, gender, marital status, education, severity of cognitive impairment (MMSE) and living with family prior to admission to the dementia facility and the dependent and relationship variables.

Inferential statistics: the following statistics will be calculated using Jamovi version 1.6.

Research Questions 1-3: Because the data are ordinal (Pittsburg Rehabilitation Participation Scale, Quality of Life Alzheimer Disease, CSDD), the Mann-Whitney U test will be used to assess differences between the intervention and control group.

Research Question 4: Because the data are ordinal (MMSE, Pittsburg Rehabilitation Participation Scale) Spearman Rank correlations will be used to determine the strength of the correlation between MMSE and Pittsburg Rehabilitation Participation Scale.

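### RQ1–3 use a valid but unadjusted Mann-Whitney U test; stratifying by MMSE severity, using day-1 QOL-AD and CSDD scores, and reporting an effect estimate with a confidence interval is a cheap improvement

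*Combined protocol and SAP*

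**What the plan says.** - **Analysis.** Data Analysis gives RQ1–3 one method because the scales are ordinal: "the Mann-Whitney U test will be used to assess differences between the intervention and control group". This covers eight comparisons: participation at two times, QOL-AD at three and CSDD at three. The only additions are alpha of .05 for every analysis and the intention-to-treat principle. The Abstract says the same for participation: "The Rank Sum test will be used to assess differences in Pittsburg Rehabilitation Participation Scale between the intervention and control group".
- **Randomisation.** Study Sequence allocates 1:1 with "randomly permuted block sizes of 2 to 6 based on severity of cognitive impairment". I read this as stratification by MMSE 10–18 versus 19–23 (the groups in Sampling), although the plan does not use that word.
- **Data collected.** All three scales are recorded "on day 1 of week 1, and on day 1 of third and sixth weeks".
- **Question asked.** RQ1 reads "What is the effect of LSQ usage on physical therapy participation in people with cognitive impairment", at 3 and 6 weeks against control; RQ2 and RQ3 have the same form.
- **Descriptive statistics.** Means, medians, standard deviations, minima and maxima are planned for the outcomes. The plan does not say they are by arm, and it gives no between-group contrast with an interval.
- **Sample size.** The trial is sized "using the Pittsburgh participation in rehabilitation scale as the primary outcome measure": difference 0.5, SD 0.5, 22 per group. QOL-AD and CSDD have no power calculation.

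**The concern.** When allocation is balanced within severity groups and severity predicts the score, an analysis that ignores severity uses too large a null variance. Its true type I error falls below the stated 0.05, and some power is lost. The plan itself makes severity a plausible predictor: Research Hypothesis 4 expects milder impairment to go with more participation. Leaving out day-1 scores likewise wastes information on QOL-AD and CSDD. Finally, a Mann-Whitney p-value does not say how large the effect is or how precisely it is known, which is what RQ1–3 ask.

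**Working it through.** **1. The plan's own figure.** Inputs from Power Analysis: d = 0.5/0.5 = 1, alpha 0.05, power 0.80. Sidedness is not stated; I take two-sided. I use a noncentral t with n multiplied by the asymptotic relative efficiency (ARE) of the Mann-Whitney test. Power of 0.80 then needs 18 per arm (36 in all) with normal scores (ARE 3/π), or 20 per arm (40) at the least favourable ARE of 0.864. So 44 does not reproduce exactly; it is more than these inputs need. At 22 per arm with normal scores, the noncentrality is 1 × √(11 × 3/π) = 3.24 on 44 × 3/π − 2 = 40.0 df, which gives power 0.885. At ARE 0.864 it is 0.851. The unadjusted test therefore meets its target for participation.

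**2. Type I error when severity is ignored.** The documents give no mild–moderate gap, so I assume g = 0.5, 1 and 1.5 within-stratum SD, with equal strata balanced across arms. With p = Φ(g/√2), strata explain a share s = 3(p − 0.5)² of the rank variance. The true type I error is then 2[1 − Φ(1.96/√(1 − s))].
- g = 0.5: p = 0.638, s = 0.057, 1.96/√0.943 = 2.02, giving 4.4%.
- g = 1: p = 0.760, s = 0.203, 1.96/√0.797 = 2.20, giving 2.8%.
- g = 1.5: p = 0.856, s = 0.379, 1.96/√0.621 = 2.49, giving 1.3%.

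Simulation agrees. The whole-point column assumes the recorded 1–6 participation scores have SD 0.5.

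| Gap | Mann-Whitney, continuous | Mann-Whitney, whole points | van Elteren |
|---|---|---|---|
| 0.5 | about 4.4% | about 4.3% | about 5% |
| 1 | about 2.6% | 3.1–3.5% | about 5% |
| 1.5 | about 1.3% | 1.7–2.6% | about 5% |

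**3. Power, Mann-Whitney / van Elteren** (continuous scores, 11 + 11 per arm, d on the total SD):

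| Gap | d = 1 | d = 0.7 (assumed) |
|---|---|---|
| 0 | 0.884 / 0.874 | 0.599 / 0.582 |
| 0.5 | 0.887 / 0.888 | 0.599 / 0.608 |
| 1 | 0.901 / 0.933 | 0.596 / 0.677 |
| 1.5 | 0.919 / 0.972 | 0.595 / 0.776 |

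On whole points at the planned effect the range is 0.89–0.93 against 0.90–0.96. Across both scales, the gain at the planned effect is nil to about 0.01, then 0.02–0.03, then 0.03–0.05 for the three gaps. At d = 0.7 it is 0.01–0.02, 0.06–0.08 and 0.10–0.18.

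**4. Day-1 adjustment (QOL-AD, CSDD).** The correlation r between day-1 and follow-up scores is assumed. The effective effect is d/√(1 − r²), with one df lost. At d = 0.7 this is 0.734, 0.808 and 0.980 for r = 0.3, 0.5 and 0.7. Power rises from 0.60 to 0.64, 0.72 and 0.87. Simulated rank-ANCOVA with stratum and no severity gap gives 0.62, 0.69 and 0.84.

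**5. Why participation is different.** Appendix B labels its first rating as before the intervention, Study Sequence says only day 1 of week 1, and the scale rates a therapy session. If the day-1 score already carried half the effect, adjusting would shrink the estimate by r/2 (15%, 25%, 35%). The effective d at a planned d of 1 would be (1 − r/2)/√(1 − r²) = 0.891, 0.866, 0.910. Power would fall from 0.885 to 0.80, 0.78 and 0.82.

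**6. The missing interval.** At d = 1 with no severity gap, the stratified probability of superiority is Φ(1/√2) = 0.76. With 22 per arm, its simulated 95% CI is typically 0.59 to 0.88, so the uncertainty is large enough to matter.

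**The case against.** **A valid, pre-specified test is not a defect.** This stands. A conservative test is not a wrong one, and a reader who infers inflated type I error has the direction reversed.

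**The gains rest on assumed figures.** This also stands. The gap, r and d = 0.7 are not in the documents. At a 0.5-SD gap and the planned effect, the gain is 0.001 on the continuous scale. Equal, perfectly balanced strata are also the extreme case: with 60 randomised and 16 random losses, type I error at a 1.5-SD gap was 2.3% rather than 1.3%.

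**A reader might infer that participation is underpowered.** Two calculations tempt that. If d = 1 refers to the within-stratum SD, a 1.5-SD gap gives the unadjusted test power of 0.74, against 0.87 stratified. If 0.5 is the SD before rounding to whole points, power is about 0.78–0.79. The documents support neither reading. They give one pilot SD and do not tie it to a stratum or to an unrounded scale. With recorded whole-point scores at SD 0.5 and no severity gap, power is 0.88–0.91.

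**The results would not be bare p-values.** Correct: descriptive statistics for the outcomes are planned. What is missing is a between-group estimate with an interval.

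**Whether scores or changes are analysed is nearly settled.** The Abstract, the power calculation and the variable list ("DV1: Pittsburg Rehabilitation Participation Scale") all point to scores. Only RQ4 speaks of improvement, without defining it. One clause closes this. It is worth adding because a change-score test at d = 1 has effective d of 1/√(2(1 − r)), with power of 0.76, 0.885 and 0.98 for r = 0.3, 0.5 and 0.7.

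**Conclusion.** The point holds as a cheap improvement. The plan uses neither the severity groups from its randomisation nor, for QOL-AD and CSDD, the day-1 scores it collects, and it plans no between-group estimate with a confidence interval. The missing estimate follows from the text alone and needs no numerical assumption. The efficiency gains depend on how far severity and day-1 scores predict follow-up. For participation at the planned effect they are at most about 0.05 of power. They matter more if the true effect is below 1 SD, and for the two outcomes with no power calculation.

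The documents do not support the stronger conclusions that the test is invalid, that participation is underpowered, or that day-1 participation scores should simply be added as a covariate. Reading the severity-based blocks as stratification is my interpretation.

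**What to change.** In Data Analysis, RQ1–3:
- **Participation:** van Elteren test stratified by MMSE 10–18 versus 19–23, with the stratified probability of superiority (same stratum weights) and its 95% CI. Do not adjust for the day-1 score unless it is confirmed to be rated before any LSQ use.
- **QOL-AD and CSDD:** once day-1 scores are confirmed to precede the first session, rank-ANCOVA on arm, day-1 rank and MMSE stratum. Report the adjusted probability of superiority (0.5 + adjusted mean-rank difference / N) with its 95% CI.
- **Missing day-1 scores:** fill with the stratum mean over both arms, so that no randomised patient is dropped. Appendix C allows QOL-AD testing to be discontinued, so this can occur.
- **Sensitivity analysis:** keep the unadjusted Mann-Whitney U test on follow-up scores.
- **Secondary wording:** state that follow-up scores are analysed, and name the 6-week assessment as primary for participation. First reconcile the Abstract (after 6 weeks of intervention) with Study Sequence (day 1 of week six).

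Cost: if severity is not prognostic, stratifying loses 0.01–0.02 of power (0.874 against 0.884 at d = 1; 0.582 against 0.599 at d = 0.7). The plan gains a second method, a fill-in rule and a timing check. The software line may need extending, because inference is assigned to Jamovi and R is named only for randomisation. No added patients or visits are needed.

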APPENDIX B: PITTSBURGH REHABILITATION PARTICIPATION SCALE

Patient name: _____

Date: _____

Instructions to therapist: for each therapy session, please circle one of each of the following to assess the patient’s participation (effort and motivation as perceived by you) in the therapy session.

Please rate as follows:

None: patient refused entire session, or did not participate in any exercises in session. (see Note below)

Poor: patient refused or did not participate in at least half of session. **Fair:** patient participated in most or all of exercises*, but did not show maximal effort or finish most exercises*, or required much encouragement to finish exercises*.

Good: patient participated in all exercises* with good effort and finished most but not all exercises* and passively followed directions (rather than actively taking interest in exercises* and future therapy).

Very good: patient participated in all exercises* with maximal effort and finished all exercises, but passively followed directions (rather than actively taking interest in exercises* and future therapy).

Excellent: patient participated in all exercises* with maximal effort, finished all exercises*, and actively took interest in exercises* and/or future therapy sessions.

Note: if patient was unable to attend therapy because of medical test, bed rest order, illness, or scheduling conflict, do not mark any score. Note: in cases of doubt, choose the lower rating, eg, “good” rather than “very good.”

Participation:

Session Number	Date	Therapist Initials	None	Poor	Fair	Good	Very good	Excellent
1 – prior to intervention			1	2	3	4	5	6
2 – 3-week			1	2	3	4	5	6
3 – 6-week			1	2	3	4	5	6
4 – 6-week following end intervention			1	2	3	4	5	6

* This version is specifically for physical therapists. For the occupational therapy form, “exercises” should be replaced by “activities”.

Source: <https://www.sralab.org/sites/default/files/2017-06/PITTSBURGH%20REHABILITATION%20PARTICIPATION%20SCALE.pdf>

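### The planned Spearman correlation for Research Question 4 names no change score, visit or arm contrast, so run on the week-6 participation level it shows neither improvement nor a difference from control

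*Combined protocol and SAP*

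**What the plan says.** Four places in the combined protocol and SAP bear on this question.

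- **Research Questions, RQ4:** the target is the "relationship between cognitive impairment severity and physical therapy participation improvement at the end of the intervention", at 6 weeks. This is a change, and no control group is mentioned.
- **Research Hypothesis 4** makes this prediction: "Mild cognitive impairment will be positively associated with participation in physical therapy at six weeks following LSQ usage as compared to a control group". This is a participation level, with a comparison against control.
- **Comparison Variables:** under the statement "The investigator plans to use the following variables (RV) for RQ 4", only the PRPS and the MMSE are listed. There is no change variable and no group term.
- **Data Analysis, Research Question 4:** "Spearman Rank correlations will be used to determine the strength of the correlation between MMSE and Pittsburg Rehabilitation Participation Scale". No change score, visit or arm is named.

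The only between-arm test in the plan is for RQ1-3, where "the Mann-Whitney U test will be used to assess differences between the intervention and control group"; it does not involve the MMSE. The rest of Data Analysis adds only an alpha of .05 and the intention-to-treat principle.

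On timing, Study Sequence has the PRPS recorded on day 1 of weeks 1, 3 and 6, with only quality of life and depression recorded six weeks after the intervention. The Appendix B form labels its first PRPS row "1 – prior to intervention" and also has a row for the post-intervention follow-up.

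**The concern.** The question, the hypothesis and the test do not share a target. A correlation between MMSE and the week-6 PRPS level mixes two things: how severity relates to participation at any time, and how severity relates to improvement. A single correlation also cannot say whether the association differs between arms.

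The risk lies in interpretation. A positive result could be reported as milder patients improving more, or gaining more from the Life Story Questionnaire (LSQ), when it reflects only an association already present on day 1. Because the text does not fix the variable or the patient set, the choice could also be made after the results are seen.

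**Working it through.** **Plan's own figures.** The plan gives no figure for RQ4. Power Analysis uses a difference between "the experimental versus the control group of 0.5 with a standard deviation of 0.5", so the effect size is 0.5/0.5 = 1, as stated. It also gives 44 patients (22 per group), but for the primary between-arm comparison. Two-sided Mann-Whitney calculations at 80% power give totals of 36 to 40, not 44. That is a separate matter; here 44 serves only as the number of patients.

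**Inputs**
- From the plan: n = 44 in all, 22 per arm; difference 0.5; SD 0.5; two-sided alpha 0.05 (sidedness is assumed); and randomization in "randomly permuted block sizes of 2 to 6 based on severity of cognitive impairment", read as balancing severity across arms.
- Assumed: the SD of 0.5 is a visit-level SD, equal at both visits within arm. Power Analysis does not say whether it is for a level or a change.
- Assumed: day-1 MMSE-PRPS correlations of 0, 0.1, 0.3 and 0.5.

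**Step 1: what the level correlation contains.** With M the MMSE and Y the PRPS, cov(M, Y6) = cov(M, Y1) + cov(M, Y6 − Y1). If MMSE does not predict change within either arm, the last term is zero and r6 = r1 × SD1/SD6.

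**Step 2: scale factor.** Pooling two equal arms that are 0.5 apart, SD6 = √(0.5² + 0.25 × 0.5²) = √0.3125 = 0.559. The factor is 0.5/0.559 = 0.894. Within the LSQ arm alone it is 1.

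**Step 3: chance of significance.** With SE = √(1.06/(n − 3)) on the Fisher z scale, the probability is Φ(atanh(r6)/SE − 1.96) + Φ(−atanh(r6)/SE − 1.96). SE is √(1.06/41) = 0.161 for n = 44 and √(1.06/19) = 0.236 for n = 22.

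| Assumed day-1 r | Pooled week-6 r | Significant, n = 44 | Significant, LSQ arm, n = 22 |
|---|---|---|---|
| 0 | 0 | 5% | 5% |
| 0.1 | 0.09 | 9% | 7% |
| 0.3 | 0.27 | 40% | 26% |
| 0.5 | 0.45 | 85% | 64% |

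MMSE has no relation to improvement in any row.

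**Step 4: check on a 1-6 scale.** This was simulated with 3,000 trials per scenario, 22 per arm, SD 0.5, scores rounded and capped to 1-6, and a baseline mean of 3.5. Pooled rates were about 34% for r = 0.3 and 77-78% for r = 0.5. If the assumed correlation applies instead to a stable underlying trait (visit-to-visit stability 0.5-0.7), they fall to 19-26% and 46-60%. Spearman with the change score rejected in 4-6% throughout, as it should when MMSE is unrelated to change.

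**Step 5: precision of the replacement.** With 1.96 + 0.84 = 2.80 for 80% power:
- n = 44: tanh(2.80 × √(1.06/41)) = 0.42
- n = 22: tanh(2.80 × √(1.06/19)) = 0.58
- Between arms: a Fisher z difference of 2.80 × √(2 × 1.06/19) = 0.94, for example rho 0 against 0.73
- An observed rho of 0.3 has a 95% interval of −0.01 to 0.55 (n = 44) or −0.15 to 0.65 (n = 22).

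**The case against.** The best reply is that Data Analysis attaches the test to RQ4, not to Hypothesis 4. RQ4 asks about improvement and, unlike RQ1-3, has no control clause. The ending of Hypothesis 4 matches that of Hypotheses 1-3 and may be carried-over wording. On this view the only fault is an unstated change score.

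Much of this stands. A reader might infer that the plan leaves level or change, and pooled or by arm, wholly open. The documents do not support that: improvement with no arm contrast is the most natural reading. It remains an inference, because both the variable list and the test name the PRPS itself.

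Two further cautions stand.

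- **The visit.** Week 6 follows from RQ4, but the timing phrase in Hypothesis 4 could also mean the post-intervention follow-up. Appendix B has a PRPS row for that time, while Study Sequence records no PRPS then.
- **The baseline.** A reader might treat the day-1 rating as certainly free of the LSQ. Only the Appendix B label suggests this. Study Sequence says day 1 of week 1, the scale rates a therapy session, and nothing states that this session is run without the LSQ.

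Finally, the rates in the table depend on assumed correlations. They are also correct detections if the target is the six-week level, which is what the level clause of Hypothesis 4 describes.

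**Conclusion.** The point holds in a limited form. RQ4 and Hypothesis 4 state different targets, and the planned statistic, as literally written, establishes neither improvement nor a difference from control. Run on the week-6 level, it would address only the level clause of Hypothesis 4.

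How misleading it could be depends on an association the documents do not give: there is no excess at a day-1 correlation of 0, and a rate of up to about 85% at 0.5 with 44 patients, with lower rates on a rounded scale or for a stable trait. A reader might take 40% or 85% as the plan's actual error rate. The documents do not support that, because those figures apply only if the level is analysed and the assumed correlation is true.

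The question is secondary and was not used to size the trial. The primary between-arm PRPS comparison is unaffected. Priority is low to moderate.

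**What to change.** 1. Align RQ4 and Hypothesis 4 on one target and name the PRPS visit. Reconcile the timing phrase in Hypothesis 4 and the follow-up PRPS row in Appendix B with Study Sequence.
2. For RQ4, report Spearman of MMSE with PRPS change (week 6 minus day 1), overall and in each arm, with confidence intervals. Show the MMSE correlation with day-1 PRPS beside it. Reconcile day 1 of week 1 in Study Sequence with the pre-intervention label in Appendix B: if the day-1 session uses the LSQ, the change score removes part of its effect.
3. Delete the control clause from Hypothesis 4. If it is kept, compare the association between arms, for example with an MMSE-by-arm interaction on week-6 PRPS adjusted for day-1 PRPS.
4. Label all of this exploratory.

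**Cost.** A few sentences in the plan, about four correlations and possibly one model; no new data are needed. The drawbacks should be stated:

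- Change scores treat an ordinal 1-6 scale as interval.
- Precision is low, as Step 5 shows.
- Near the ceiling (assumed baseline mean 5, correlation 0.5, stability 0.7) with SD 1, the change-score tests rejected in about 10-21% of null simulations and the linear interaction in 12-17%. With SD 0.5 these rates were 5-6%.
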